8.4 Accrual Goal and Accrual Period

To help safeguard 10 enrolling sites per intervention group (as originally proposed), we have invited more than 20 MU NCORPs/NCORPs to participate in this study (as listed on the cover page of the protocol). To further help accrual, we lowered the age limit to 15 years in Addendum 9 (effective from February 6, 2019). Besides the original participating MU NCORPs/NCORPs, interested pediatric MU NCORPs/NCORPs are allowed to participate in the EROS trial as well.

To have adequate power to detect the difference from 50% to 80% in the primary endpoint, the accrual goal of this study was re-calculated to ensure 149 patients in the intervention arm, assuming 16 sites enrolling patients for this trial (8 to the non-intervention group (Arm A) and the other 8 to the intervention group (Arm B)). Patients from each site will be enrolled into one of the four strata depending on the patient's pregnancy status, sexual activity status, and/or her birth intention. Given some sites accrue much faster than the others, a NCORP accrual cap of 45 patients was implemented per Addendum 8.

As of January 4, 2021, 268 patients from 9 Arm A sites and 138 patients from 8 Arm B sites have had been enrolled to this trial. As this is a comparative study, the trial will continue accrual for both arms until Arm B meets its accrual goal of 149 patients which is projected to take another 5 months. Taking into account the site accrual up to January 4, 2021 and the accrual rate in the past three months (i.e., the last three months of 2020, with the top three accrual sites met the accrual cap of 45 patients and closed accrual to Arm A), the final accrual of this study, thus, is expected to be 425 patients (276 from Arm A and 149 from Arm

Rev. Add11

Rev. Add8
Rev. Add9

B). The mean cluster size is projected to be 25 patients assuming 17 enrolling sites in total (~30 patients per cluster for Arm A and ~18 patients per cluster for Arm B). As suggested by Table 1, this study is equipped with more power if the cluster size is larger than the average of 18-19 patients per cluster and/or if the number of clusters per arm is greater than the stated 8 sites per arm in the sample size calculations. The additional patients and sites in Arm A imply the power of this study will be a little larger than stated (i.e., 85% power) to detect a change from 50% to 80% on the primary endpoint with the projected final accrual of 425 patients.

Based on E5103, PACT1, E4599, and E4402, it is projected that the accrual rate for this patient population (female patients initially diagnosed with any form of cancer within the reproductive age of 15-55) is 50 patients per month. Since only limited institutions will be invited to participate in this study, it is further assumed that 13 patients per month will be accrued via these institutions for this study.

8.5 Power for the Important Second Endpoint (the LTC Usage at 6 Month Assessment)

8.5.1 Stratum 1 with patients who are not pregnant, sexually active, and have not completed childbearing.

It is expected that intervention can increase the LTC usage rate at 6 months after baseline visit from 1% (without intervention) to 22% for patients in Stratum 1.

Table 2 shows the power with various parameter values to detect such an improvement, assuming $ICC=0.10$, an exchangeable within-cluster correlation structure, t-distribution, and type I error rate at 0.10 (two-sided). As indicated in Table 2, this study needs an average of 10 eligible patients enrolled into stratum 1 per cluster in order to have 84% power to detect an improvement in the LTC usage rate at 6 months from 1% to 22%, assuming $ICC=0.10$, 8 institutions per arm, and $CV=0.8$. The power drops to 47% if an average of 3 eligible patients is enrolled into stratum 1 per cluster, keeping all other parameters constant.

Results from the fourth interim analysis suggest that approximately 20% of eligible patients can be categorized into Stratum 2 and the 6-month attrition rate is approximately 20%. With the stated 15 eligible patients to detect a change from 50% to 80% on the primary endpoint (assuming 8 sites per arm), the projected average cluster size is 2-3 eligible patients in stratum 1 ($=15 \times 0.2 \times 0.80$). Thus, the new study design is not adequately powered to detect the proposed difference in LTC usage rate in Stratum 1.

Table 2: Power for Various Plausible Parameter Values (assuming improvement from 1% to 22%, $ICC=0.10$, an exchangeable within-cluster correlation structure, t-distribution, and $\alpha=0.10$).

Number of Clusters (k, per arm)	Coefficient of Variation (CV)	Mean Cluster Size (m)	Power
8	0.5	3	0.50
	0.5	4	0.65

Number of Clusters (k, per arm)	Coefficient of Variation (CV)	Mean Cluster Size (m)	Power
	0.5	5	0.73
	0.5	10	0.89
	0.8	3	0.47
	0.8	4	0.61
	0.8	5	0.69
	0.8	10	0.84
10	0.5	3	0.59
	0.5	5	0.82
	0.5	10	0.94
	0.8	3	0.56
	0.8	5	0.77
	0.8	10	0.90

8.5.2 Stratum 2 with patients who are not pregnant, sexually active, and have completed childbearing

It is expected that intervention can increase the LTC usage rate at 6 months after baseline visit from 20% (without intervention) to 60% for patients in Stratum 2. Table 3 summarizes the power with various parameter values, assuming ICC=0.10, an exchangeable within-cluster correlation structure, t-distribution, and type I error rate at 0.10 (two-sided). As indicated in Table 3, this study needs an average of 5 eligible patients enrolled into stratum 2 per cluster in order to have 85% power to detect an improvement in the LTC usage rate at 6 months from 20% to 60%, assuming ICC=0.10, 8 institutions per arm, and CV=0.8.

Results from the fourth interim analysis suggest that approximately 40% of eligible patients can be categorized into Stratum 2 and the 6-month attrition rate is approximately 20%. With the stated 15 eligible patients to detect a change from 50% to 80% on the primary endpoint (assuming 8 sites per arm), the projected average cluster size is expected to be 4-5 eligible patients in stratum 2 ($=15 \times 0.4 \times 0.8$). Consequently, the new study design has at least 80% power to detect an increase from 20% to 60% in the LTC usage rate at 6 month between the two arms.

Table 3: Power for Various Plausible Parameter Values (assuming improvement from 20% to 60%, ICC=0.10, an exchangeable within-cluster correlation structure, t-distribution, and $\alpha=0.10$)

Number of Clusters (k, per arm)	Coefficient of Variation (CV)	Mean Cluster Size (m)	Power
8	0.5	3	0.71
	0.5	4	0.84
	0.5	5	0.89

Number of Clusters (k, per arm)	Coefficient of Variation (CV)	Mean Cluster Size (m)	Power
	0.5	10	0.97
	0.8	3	0.67
	0.8	4	0.80
	0.8	5	0.86
	0.8	10	0.95
10	0.5	3	0.79
	0.5	5	0.94
	0.5	10	0.99
	0.8	3	0.76
	0.8	5	0.92
	0.8	10	0.98

Rev. Add8 8.5.3 Stratum 3 with patients who are not pregnant and not sexually active
Stratum 3 is an observational group and no specific hypothesis is proposed for it.

Rev. Add10 8.5.4 Stratum 4 with pregnant patients and patients who are interested in becoming pregnant within one year of study enrollment.
Stratum 4 is an observational group and no specific hypothesis is proposed for it.

8.6 Analysis Plan

8.6.1 Plan for the primary objective
With a cluster randomized design, the generalized estimating equations (GEEs) method will be used to evaluate the intervention effect. The GEEs method can be used to construct an extension of standard logistic regression²⁷. For the primary endpoint, appropriate reproductive health management, a GEE model with an exchangeable correlation structure (i.e., assuming every patient within a cluster is equally correlated with every other patient from that cluster) and registering institution as the cluster variable will be fitted to compare the rates between the intervention group and the no intervention group by combining patients in all strata. The appropriate reproductive health management rate at each time point will be summarized, by arm, with frequency and percentage along with its 95% confidence interval. This rate in the non-intervention arm will indicate whether reproductive health needs are adequately addressed (Hypothesis 1, Section [1.4.1](#)). Whether the intervention can improve reproductive health care (Hypothesis 2, Section [1.4.2](#)) can be determined by comparing this rate between the non-intervention arm and the intervention arm.

The same method will be used to evaluate the intervention effect on contraception usage for Stratum 1 and Stratum 2, separately. Since it is expected that contraception usage will be influenced by the number

of children (0, 1-2, >2), type of treatment (chemo vs. RT vs. surgery vs. combination), and disease stage (nonmetastatic vs. metastatic) as well, these factors will be included in the model as covariates. The contraception usage rate at each time point will be reported with frequency and percentage along with its 95% confidence interval. Similar analysis method will be applied to the proportion of patients with pregnancy by the end of 2 years after baseline visit on the study. The analysis will be applied to patients by stratum for each of these secondary endpoints.

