8.3 Sample Size

To have a manageable number of patients in this study, the sample size is recalculated based on the primary endpoint. For a cluster randomized trial, we must take into account the similarity among responses within a cluster (known as the intracluster correlation coefficient (ICC); ICC=0 indicating individuals completely independent; ICC=1 indicating individuals completely dependent), the required number of clusters per arm (denoted as k), and the number of patients per cluster (denoted as m) for the sample size calculations. To account for the possibility of variable cluster size in real accrual, coefficient of variation (CV) of cluster sizes (defined as the ratio of standard deviation of cluster sizes to mean of cluster sizes) was considered in sample size calculations as well. In this section, the power is computed assuming equal enrollment per arm. As of January 4, 2021, though, 66% (268/406) of the enrollment is from sites on the control arm and 34% from sites in the intervention group (with recent accrual closer to 50% in each group, due to site accrual caps). The number of intervention arm cases needed under equal enrollment will then be used to determine the overall sample size under the enrollment proportions seen in this study. The actual power should then be higher than stated, given the additional enrollment on the control arm.

To detect an increase from 50% to 80% (across all four strata) in the adoption of appropriate reproductive health management within 3 months consistent with patient's initial reproductive health goals (the primary endpoint), Table 1 shows the power with respect to various parameter values (including intra-cluster correlation coefficient, number of clusters, coefficient of variation, and mean cluster size), assuming an exchangeable within-cluster correlation structure, t-distribution, and type I error rate (α) at 0.10 (two-sided). The sample size and power calculations were conducted using the Shiny CRT Calculator, a web-based tool (<https://clusterrcts.shinyapps.io/rshinyapp/>)^{24,25}.

Table 1: Power for Various Plausible Parameter Values (assuming an exchangeable within-cluster correlation structure, t-distribution, and $\alpha=0.10$)

Number of Clusters (k, per arm)	Coefficient of Variation (CV)	Mean Cluster Size (m)	ICC		
			0.05	0.10	0.15
8	0.0	11	0.96	0.90	0.84
	0.5	14	0.97	0.90	0.82
	0.6	16	0.97	0.90	0.81
	0.7	20	0.98	0.90	0.81
	0.8	15	0.95	0.85	0.75
	0.8	27	0.98	0.90	0.80
9	0.0	9	0.95	0.90	0.85

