	0.5	11	0.96	0.90	0.83
	0.6	12	0.96	0.90	0.82
	0.7	14	0.97	0.90	0.82
	0.8	17	0.97	0.90	0.81
10	0.0	8	0.96	0.91	0.87
	0.5	9	0.96	0.90	0.84

Number of Clusters (k, per arm)	Coefficient of Variation (CV)	Mean Cluster Size (m)	ICC		
			0.05	0.10	0.15
	0.6	10	0.96	0.90	0.84
	0.7	11	0.97	0.90	0.83
	0.8	12	0.97	0.90	0.81

Based on the results in the Verma and Lê's study²⁶, it is estimated that the intra-cluster correlation coefficient for the primary endpoint is 0.10. As of January 4, 2021, 9 Arm A sites and 8 Arm B sites have had enrolled patients for the EROS trial (n=268 for Arm A and 138 for Arm B) with CV=0.78 (=23.9/18.6). Assuming ICC=0.10, 16 institutions in total (i.e., 8 clusters per arm) and CV=0.8, Table 1 indicates an average of 27 eligible patients per cluster can detect an improvement from 50% to 80% while keeping 0.10 two-sided type I error rate and 90% power. Due to the slow accrual in Arm B, the study power was lowered to 85% with an average of 15 eligible patients per cluster, keeping the other parameters constant. In this case, this study requires 240 eligible patients in total enrolled into this study (average of 15 per cluster, 120 per arm) in order to keep 0.10 type I error rate and 85% chance of detecting the proposed 50% to 80% improvement on the primary endpoint. Assuming a 5% ineligibility rate and an additional 15% of attrition rate at 3 months (based on the fourth interim analysis with data pulled in July 2019), the sample size for the primary endpoint of this study is inflated to 298 patients in total (149 patients per arm, across the four strata), under equal enrollment on the two arms. To obtain 149 intervention arm cases, total enrollment will need to be 425 patients (see below).

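### Section 8.6.1 states no standard error, small-sample correction or reference distribution for the primary GEE on 16–17 unequal clusters; with the uncorrected sandwich SE, the nominal 10% error becomes about 13–17%

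*Combined protocol and SAP*

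**What the plan says.** Section 8.6.1 tests the primary endpoint with a GEE: "The GEEs method can be used to construct an extension of standard logistic regression". The model has an exchangeable correlation structure, with "registering institution as the cluster variable will be fitted to compare the rates between the intervention group and the no intervention group", all strata combined. The same method is then applied to contraception use in Strata 1 and 2. Nothing there, or in Sections 8.7, 8.8 or 8.10, says whether the SE is robust or model-based, whether it is corrected for few clusters, or which distribution the test statistic is referred to.

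A reference distribution is mentioned only for power. Section 8.3 computes Table 1 "assuming an exchangeable within-cluster correlation structure, t-distribution, and type I error rate (α) at 0.10 (two-sided"), and Sections 8.5.1 and 8.5.2 repeat the assumption: "an exchangeable within-cluster correlation structure, t-distribution, and type I error rate at 0.10 (two-sided").

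The design has few, unequal clusters. The sample size is set by "Assuming ICC=0.10, 16 institutions in total (i.e., 8 clusters per arm) and CV=0.8" with a mean of 15 eligible patients per cluster. Section 8.3 also reports 9 Arm A and 8 Arm B sites enrolling, with an observed CV of 0.78. Section 8.4 projects 276 patients in Arm A and 149 in Arm B: "The mean cluster size is projected to be 25 patients assuming 17 enrolling sites in total". Section 8.1 places endpoint details in a statistical analysis plan in Addendum II, which was not among the documents available.

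**The concern.** The sandwich variance replaces the unknown cluster-level variance with squared residuals from the fitted model. Each cluster pulls the fit towards itself, so the residuals are too small. With many clusters this is negligible, but with eight per arm it is not, and unequal sizes make it worse because a few large clusters carry high leverage. A normal reference adds to the error by ignoring the uncertainty in the estimated variance.

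An analyst following 8.6.1 as written could use an uncorrected SE with a normal reference, an uncorrected SE with t, or a corrected SE with t, and each would comply. The true error of these choices ranges from about 8% to 17% against a stated 10%. If the choice stays open until data are in hand, the trial's error rate is not fixed in advance.

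**Working it through.** **Inputs from the plan.** Two-sided α 0.10; ICC 0.10 (Table 1 of Section 8.3 also shows 0.05 and 0.15); 50% v 80%; 8 clusters per arm, mean 15, CV 0.8; 9 and 8 sites enrolling; projected enrolment 276 and 149; 5% ineligible and 15% lost by 3 months; site cap 45.

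**1. The plan's power figure.**
- Design effect = 1 + [(1 + CV²)m − 1] × ICC = 1 + (1.64 × 15 − 1) × 0.10 = 3.36.
- SE = √[(0.25 + 0.16) × 3.36 / 120] = 0.107; effect/SE = 0.30/0.107 = 2.80.
- With t on 14 df (critical value 1.761), power = 0.842, or 0.845 by noncentral t, against the stated 0.85. With a normal reference (1.645) and the same unpooled variance it is 0.876.

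The stated figure agrees with the t-distribution that Section 8.3 says it used. It does not prove it, since a pooled variance with a normal reference gives 0.844.

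**2. Projected evaluable cluster sizes.**
- Arm A: 276 × 0.95 × 0.85 / 9 = 24.8.
- Arm B: 149 × 0.95 × 0.85 / 8 = 15.0.
- Cap: 45 × 0.95 × 0.85 = 36.

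**3. Within-arm CV.** The mean is 406/17 = 23.9, so 18.6 is read as the SD and the ratio in Section 8.3 as printed upside down (18.6/23.9 = 0.78).
- Total sum of squares = 16 × 18.6² = 5535; the between-arm part (268/9 = 29.8 v 138/8 = 17.25 per site) = 665; remainder about 4871.
- Common within-arm CV = √[4871 / (8 × 29.78² + 7 × 17.25²)] = 0.73.

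Results are therefore given for CV 0.7 and 0.8.

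**4. Closed form.** With arm as the only covariate, cluster weight w = n/[1 + (n − 1)ρ] and leverage h = w/Σw within arm. The sandwich variance of an arm's rate is Σh²(cluster rate − arm rate)². Kauermann-Carroll divides each term by (1 − h), Mancl-DeRouen by (1 − h)². With eight equal clusters h = 1/8, so the uncorrected variance averages 7/8 = 0.875 of the true value, and the SE is about √0.875 = 0.94 of what it should be. Unequal sizes worsen this. On three test datasets the closed form matched a standard GEE routine: robust SE 0.3307, 0.5714, 0.4609; Mancl-DeRouen SE 0.3844, 0.6588, 0.5481 (ratios 1.16, 1.15, 1.19).

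**5. Simulated type I error of the uncorrected sandwich SE.** Null 50% v 50%, nominal 10%, ICC 0.10, beta-binomial outcomes, gamma-Poisson cluster sizes, 20,000 datasets per scenario (Monte Carlo SE about 0.3 points). Entries are CV 0.7 / CV 0.8.

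| Design | Normal reference | t(K−2) |
|---|---|---|
| 8 v 8, mean 15 | 16.4 / 17.0% | 13.8 / 14.4% |
| 9 v 8, means 24.8 and 15 | 15.3 / 15.7% | 12.9 / 13.4% |
| 9 v 8, clusters cut at 36 | 15.3 / 15.9% | 13.1 / 13.5% |

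- ICC 0.05–0.15 and CV 0.6–0.8: 14.4–18.4% (normal), 12.1–15.8% (t).
- Equal cluster sizes within arm: 13.5–14.4% (normal), 11.2–12.2% (t).
- An independently coded simulation at CV 0.8 gave 17.0% and 14.5% for 8 v 8, and 15.4% and 13.1% for 9 v 8. In it the model-based SE was similarly inflated with unequal clusters: 15.3–17.2% (normal), 12.9–14.7% (t).

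**6. Corrected SEs with t(K−2), ICC 0.10, CV 0.7–0.8.** Power is for 50% v 80%, CV 0.7 / 0.8.

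| SE | Type I error | Power, 8 v 8 | Power, 9 v 8 |
|---|---|---|---|
| Mancl-DeRouen | 8.3–9.0% | 85.0 / 83.7% | 88.9 / 87.4% |
| Kauermann-Carroll | 10.6–11.7% | 88.0 / 87.4% | 91.3 / 90.3% |

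Over the wider ICC and CV grid, error was 7.9–9.4% for Mancl-DeRouen and 9.9–12.2% for Kauermann-Carroll.

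**The case against.** - **Addendum II may already settle it.** An SE and degrees of freedom are normal content for a separate analysis plan, so the omission can be asserted only for the text available. That stands. But Section 8.1 cites the addendum for endpoint details, withheld to protect control sites. An SE reveals nothing about the intervention, so that rationale gives no reason to leave it out of 8.6.1.
- **No stated analysis is shown to be wrong.** Also true: the inflation applies only if an uncorrected SE is used. But the uncorrected sandwich and the model-based SE are the ordinary ways to run this model, and both exceed 10%.
- **The power sections assume t, so t is the natural reading, and 17% belongs to the 8 v 8 planning scenario with a normal reference.** Fair. For the projected 9 v 8 design with t, the figure is about 13%, an excess of roughly 3 points. That is smaller, but not removed.
- **Mancl-DeRouen with t is conservative, and other corrections are defensible.** Correct. Kauermann-Carroll with t, or Mancl-DeRouen with a normal reference (10.2–11.0% at CV 0.8 over ICC 0.05–0.15), lies closer to 10%. The need is to name one choice; which one is a judgement for the trial statisticians.

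**Conclusion.** The concern holds. Section 8.6.1 leaves open a choice that decides whether the 0.10 level is met. With the uncorrected sandwich SE at ICC 0.10, actual error is about 15–17% (normal) or 13–14% (t), and at the projected 9 v 8 it is about 15–16% or 13%. The ICC is the plan's own. The beta-binomial outcomes, gamma-Poisson cluster sizes and 50% null rate are assumptions. Equal cluster sizes would shrink the excess, while a null rate of 80% raises it somewhat (17.7% and 15.0% at 8 v 8, CV 0.8). The finding is limited to the available text, and a suitable specification in Addendum II would resolve it. It should be settled before the primary comparison is run.

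**What to change.** Add one sentence to 8.6.1 that pre-specifies a single bias-corrected sandwich SE for the arm effect, referred to a t-distribution with degrees of freedom equal to the number of randomised NCORP groups contributing data minus 2, at two-sided 0.10. Mancl-DeRouen is the safer default if the level must be held, as it stayed below 10% in every scenario simulated. Kauermann-Carroll trades a slight excess for more power. If Addendum II already specifies such a correction, a cross-reference is enough.

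The cost is wording only; the GEE model and sample size stay as planned. Intervals widen (the Mancl-DeRouen SE was 15–19% larger than the uncorrected SE in the three check datasets). At 8 v 8, Mancl-DeRouen power is 83.7–85.0% against the stated 85%.

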1.4 Hypotheses

- 1.4.1 The reproductive health needs for females with cancer are not adequately assessed and addressed by cancer care providers.
- 1.4.2 The implementation of the proposed reproductive health assessment and algorithm will optimize the reproductive health objectives of females with cancer.
- 1.4.3 Patients and clinicians have different perspectives regarding reproductive health objectives of females with cancer.
- 1.4.4 There are certain clinical, demographic, healthcare delivery, and socioeconomic factors that affect patients with regards to adequacy of reproductive health management.

Rev. Add9

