4.1 Selection and Randomization of Sites

To ensure patient diversity in this study, all Minority/Underserved National Cancer Institute Community Oncology Research Programs (MU NCORP) sites will be invited to participate. The remainder of sites will be filled by NCORPs.

All MU NCORPs and selected NCORPs will receive an invitation letter from the Group Chair together with the study chair including a brief description of the study. Potential sites will be asked to respond to several questions related to site

characteristics, including patient volume and possible accrual and reproductive-related services available in the areas of each site, to determine feasibility of utilizing the site for trial recruitment and the site's level of interest in serving as a study site. Information from sites that respond will be reviewed by the study chair and the study team. Sites that express interest in participating and that report adequate patient volume to meet the protocol accrual goal will be sent a formal invitation to participate in this study. Depending on the number of participating MU NCORPs, other NCORPs will be randomly selected to participate in this study. Once sites have been selected, they will be randomized to the intervention or non-intervention arm. Sites randomized to the intervention arm will receive access to additional materials and information specific to the intervention including the intervention content.

A notice of randomized intervention assignment will be forwarded by the ECOG-ACRIN Operations Office - Boston. Each participating institution will be sent a notice confirming the assignment of the intervention or non-intervention arm.

Rev. 11/17

Rev. Add8

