5.4 Patient Recruitment

Patients from oncology clinics with newly diagnosed cancer are possible candidates for the study. Complete eligibility criteria are included in Section [3](#). After the diagnosis of cancer is given to the patient, the primary provider will refer the patient to the study personnel for initial contact. The primary provider is defined as the clinician (MD, nurse practitioner, PA-C) that is clinically assessing the oncology patient. Subjects must enroll prior to initiation of chemotherapy or radiation, if applicable.

Institutions will identify a clinical research nurse (CRN)/CRA that will be responsible for all aspects of this study. The designated (CRN)/CRA from each institution will be available to work with physicians during the clinical session to identify and recruit patients. This person will discuss the details of this study with appropriate care and thoughtfulness as she has recently received the diagnosis of a cancer. If the patient agrees, she will be screened for study eligibility at that time or at a subsequent visit as deemed appropriate by study personnel. This person will also be available to answer any questions regarding the study.

Patients will either be enrolled in the study or listed on the “Patient Log” ([Appendix II](#)), which requires a reason for the patient’s decision not to participate. Please keep a copy of the Patient Log in patient chart at institution.

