5.5 Data Collection

Patients will be followed over time and all surveys will be administered as described in Table 1 (Section [7](#)).

Rev. 11/16

- 5.5.1 Following site randomization and local IRB approval, a consent form will be given to each provider (oncology staff, i.e. MD, nurse practitioner or PA-C, that clinically assesses the patient). A signed provider consent form is required for participation.
- 5.5.2 Upon site study activation a delegation of responsibility log should be completed and submitted to CTSU prior to enrolling the first patient
- 5.5.3 Patients will be recruited to participate at their scheduled provider appointment. Study staff will approach patients who are possible candidates to determine interest. If interested, eligibility will be confirmed (Section [3](#)).

Rev. 11/17

- 5.5.4 A consent form will be given to interested and eligible patients. The consent form should be completed on the same day eligibility is confirmed, however, it must be signed prior to treatment initiation (See Section [7](#) Patient-specific timeline).
- 5.5.5 Patient will have the baseline provider visit, complete baseline surveys and be registered to the trial on the same day of consent. If this is not feasible, then all baseline requirements (including registration) must be completed within one week of patient consent. Baseline provider visits, completion of baseline surveys and study registration must be completed on same day. (Table 1).
- 5.5.6 The designated research staff person (CRN or CRA) from each institution will administer questionnaires and assist with the completion of form(s) at the baseline and follow-up visits, as necessary. A CRN or CRA must review form(s) for completeness as

soon as the patient finishes them to ensure all items have been marked appropriately.

- 5.5.7 The scheduled study tools must be completed during the visit.
- 5.5.8 Completed clinician and patient form(s) will be entered into Medidata Rave within 7 days of collection.

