Rev. Add8	The primary objective of this study is to evaluate the success of implementation of the reproductive health programming among females aged between 15-55 years old with initial diagnosis of any form of cancer (before chemotherapy or radiation has started). Secondary objectives include (1) assessing the degree of discrepancy between patients and their clinicians in estimates of significance of the reproductive health goals for the patient, (2) evaluating baseline and follow-up reproductive health assessments for trends in reproductive health choices relating oncofertility, oncocontraception, and pregnancy over the 2 year study period, (3) identifying clinical and demographic factors that predict the adequacy of reproductive health management.
Rev. Add9	
Rev. Add11	
Rev. 11/17	E1Q11 is a cluster randomized trial (CRT) with patients in one site all receiving the same intervention. This study was originally designed with a paired-matching cluster randomization, paired mainly by the type of institution (MU NCORP vs. NCORP) and geographical region (Northeast vs. Midwest vs. South vs. West). However, this design falls apart as some sites originally invited to participate in this study dropped from the study (at various time points). Consequently, the study design is now changed to a parallel cluster randomization (i.e., with clusters randomized to one of treatment arms). To have a manageable number of patients in this study and have this study completed in a reasonable timeline, the sample size was re-calculated based mainly on the primary endpoint of the primary objective (instead of the important secondary endpoint of the primary objective) and the patient's age limit was lowered to 15 years. Due to an oversight in previous sample size calculations, the sample size was re-calculated in amendment 13.
Rev. Add8	
Rev. Add9	8.1 Design and Randomization

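### The primary GEE names no baseline covariate, although patients are referred by providers at sites that already know their arm, so systematic differences in recruited case mix would enter the primary comparison unadjusted.

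*Combined protocol and SAP*

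**What the plan says.** Section 8.6.1 specifies, for appropriate reproductive health management, a GEE with exchangeable correlation and registering institution as the cluster, which "will be fitted to compare the rates between the intervention group and the no intervention group by combining patients in all strata". No covariate is named. The next paragraph, on contraception usage, lists number of children, type of treatment and disease stage and states that "these factors will be included in the model as covariates".

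Elsewhere the plan treats baseline factors as relevant to the primary outcome. Hypothesis 4 (section 1.4.4) reads "There are certain clinical, demographic, healthcare delivery, and socioeconomic factors that affect patients with regards to adequacy of reproductive health management". Section 8.6.2 studies such factors with a GEE under Objective 3, but as predictors, not as adjustment of the arm comparison.

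On the order of events, section 4.1 says "Each participating institution will be sent a notice confirming the assignment of the intervention or non-intervention arm", and section 5.5.1 says "Following site randomization and local IRB approval, a consent form will be given to each provider". Section 5.1 restricts intervention training to Arm B sites. Under section 5.4, once a patient has her diagnosis, "the primary provider will refer the patient to the study personnel for initial contact".

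The opening of section 8 explains that the design originally matched sites, "paired mainly by the type of institution (MU NCORP vs. NCORP) and geographical region", and that matching was abandoned when sites dropped out. Section 8.7 describes simple 1:1 allocation of sites and names no stratification. Section 8.4 reports "268 patients from 9 Arm A sites and 138 patients from 8 Arm B sites" as of 4 January 2021.

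**The concern.** Cluster randomisation balances sites in expectation. It does not protect the mix of patients within sites when the people who refer them already know the arm. A provider who has been through reproductive health training may refer different patients from one who has not. If those patients differ in age, stage, childbearing intention or other factors related to adequate management, the arm comparison mixes the intervention effect with the difference in who was recruited. The stated primary model has no term that would remove any of this, and the matching that once balanced institution type and region is gone.

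At stake are the type I error and the size of the estimated effect on the primary endpoint. There may also be a loss of precision from leaving out prognostic variables that are already collected. That loss is not quantified here.

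**Working it through.** **1. The plan's own figures (section 8.3).** Inputs: 50% vs 80%, 8 clusters per arm, mean size 15, CV 0.8, ICC 0.10, two-sided alpha 0.10, t-distribution.

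- Design effect = 1 + ((0.8² + 1) × 15 − 1) × 0.10 = 1 + (24.6 − 1) × 0.10 = 3.36.
- Planned-alternative SE = √[(0.25 + 0.16)/120 × 3.36] = 0.107.
- Power with t on 14 df is about 84%, against 85% stated.
- Inflation: 240/(0.95 × 0.85) = 297.2, or 148.6 per arm, which rounds to the stated 149 per arm and 298 in total.

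The planning figures reproduce, so the SE is a fair yardstick.

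**2. False difference from case mix.** False difference = (between-arm shift in a stratum's share) × (gap in outcome rate between strata). The documents give neither quantity for the primary endpoint, so both are assumptions. A 30-point gap with a 10 to 20 point shift gives 0.30 × 0.10 = 3 points to 0.30 × 0.20 = 6 points. Wider ranges (gaps of 20 to 50 points, shifts of 5 to 20) give 1 to 10 points. The nearest figures in the documents are the planning rates for long-term contraception in section 8.1: Strata 1 and 2 differ by 20 − 1 = 19 points without intervention and 60 − 22 = 38 points with it. That is a different endpoint, so it shows only that a 30-point gap is not absurd.

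**3. Effect on the 0.10 error.**

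| SE used | SE (points) | Reference | Error, 3-point false difference | Error, 6-point false difference |
|---|---|---|---|---|
| Planned alternative | 10.7 | normal | 0.113 | 0.153 |
| Null, 50% in both arms: √[(0.25 + 0.25)/120 × 3.36] | 11.8 | t, 14 df | 0.110 | 0.139 |

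The second row is the more coherent one, because type I error is a null quantity and section 8.3 assumes a t-distribution.

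**4. Projected enrolment (section 8.4: 276 and 149 patients, 9 and 8 sites).** After 5% ineligibility and 15% attrition this leaves about 223 and 120 evaluable patients. With a null SE of 11.2 points and t on 15 df, biases of 2, 5, 8 and 10 points give errors of 10.5%, 13.1%, 17.8% and 22.0%.

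**5. Simulation of the exchangeable GEE.** Settings: no true effect, 9 vs 8 sites, ICC about 0.10, CV 0.8, bias-reduced SE, 600 replicates per scenario, assumed stratum shares and rates.

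| Imbalance | False difference | Unadjusted rejection | Stratum-adjusted rejection |
|---|---|---|---|
| None | about 0 | 10.2% | 8.8% |
| 10-point shift | about 4 points | 9.7% | 9.0% |
| 20-point shift | about 6 points | 14.8% | 10.0% |

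In the last scenario the median log odds ratio moved from 0.25 unadjusted to 0.02 adjusted. Monte Carlo error near 10% is √(0.1 × 0.9/600) = 1.2 points, so a false difference of about 4 points produced no detectable inflation.

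**The case against.** An unadjusted marginal GEE is a legitimate primary analysis for a cluster trial, and several stronger readings fail.

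- **Chance imbalance.** A reader might infer that any imbalance in case mix biases the result. It does not. Chance differences between sites are part of between-cluster variation, and the nominal error already covers them. Only systematic selection is a bias.
- **Two-to-one enrolment.** A reader might take 268 vs 138 as evidence of selection. Unequal numbers do not bias the comparison. Section 8.4 says that the three top-accruing sites reached the cap of 45. If these are Arm A sites, they hold at least 3 × 45 = 135 of its 268 patients. The other six then average at most 133/6 = 22, against 138/8 = 17 in Arm B. Section 8.3 adds that recent accrual is closer to equal. A few fast sites could explain much of the gap, and nothing in the documents shows that the arms recruited different kinds of patient.
- **Rates by stratum.** The endpoint scores each patient against her own initial goals (section 8.3), which could narrow differences between strata as easily as widen them. Hypothesis 4 does not name stratum or give a size.
- **Certainty about the model.** A reader might conclude that the model contains arm alone, or that the old matching factors are used nowhere. Combining strata describes the population analysed and does not exclude a stratum term. Section 8.1 also refers to a statistical analysis plan in Addendum II, which is not in the available text.
- **Adjusting for stratum.** Stratum depends partly on birth intention, and note 9 to Table 1 in section 7 places the baseline interview after the provider visit. If that interview assigns stratum at a site that knows its arm, stratum may itself be affected by arm.

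All five stand as limits on the claim. They do not remove the route by which selective referral could affect the comparison, or explain why the secondary model is adjusted and the primary one is not.

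**Conclusion.** The point holds in a limited form. As section 8.6.1 is written, the primary comparison has no stated protection against systematic differences in case mix, in a design where providers at sites aware of their arm choose whom to refer. The plan itself expects baseline factors to matter.

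The actual bias cannot be determined: the documents give neither stratum mix by arm nor primary rates by stratum, and its direction is unknown. Under the assumed false differences of 3 to 6 points the error is about 0.11 to 0.15, or 0.11 to 0.14 on the null-variance calculation. That is modest, and small to moderate beside the 30-point target effect. The reason to act is that a better analysis is available from baseline data at almost no cost, not that the primary result is shown to be invalid.

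**What to change.** Before arm-level outcomes are analysed, amend section 8.6.1 to:

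1. Make the primary GEE adjust for a few baseline variables that the arm cannot affect: age, disease stage and institution type (MU NCORP vs NCORP).
2. Add stratum to that model if it is confirmed to be recorded before any intervention exposure. Otherwise use it only in a sensitivity analysis.
3. Use a small-sample-corrected variance suited to about 17 clusters.
4. Report the standardised marginal difference in rates, so that the effect stays on the scale of the 50% vs 80% hypothesis.
5. Keep the unadjusted GEE as a sensitivity analysis.
6. Tabulate stratum mix and baseline characteristics by arm.

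If Addendum II already names covariates for the primary model, reconcile section 8.6.1 with it.

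The cost is SAP wording and a little more analysis, with no added patients. Institution type uses one between-site degree of freedom (with 17 sites, from 17 − 2 = 15 to 14). Adjustment removes only measured differences; unmeasured selection by providers would remain and should be acknowledged as a limitation.
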